9.7.1.6.1 PRIMARY EFFICACY ANALYSIS

Primary analysis of primary endpoint

The primary analysis will be based on MCI/Prodromal subjects from the FAS with the prespecified censoring rule applied. The primary endpoint is the change from baseline to 18 months in the derived ADCOMS. The dose-response of the primary endpoint is modelled with a first-order normal dynamic linear model, where Normal and Inverse-Gamma priors are used. The primary efficacy analysis will calculate the Bayesian posterior probability that the dose identified is the most likely ED₉₀ dose that achieves 25% improvement over the placebo arm. At each interim analysis and the final analysis, 2 Bayesian probabilities will be summarized for each active dose: the probability it is the ED₉₀ dose and the probability of achieving 25% improvement over the placebo arm.

For the clinical efficacy data (ie, derived ADCOMS, MMSE, CDR, ADAS-cog, CBB, ISLT, and FAQ) subjects will be censored at the time of initiation of treatment with AChEIs or memantine, if they were not on these medications at the time of Baseline cognitive assessment (Visit 2), and will be censored at the time of dose adjustment of AChEIs or memantine if they were already on stable treatment with these medications at the time of Baseline cognitive assessment (Visit 2). The value of the primary endpoint for censored subjects will be imputed using data up to the censoring time and Bayesian longitudinal modeling.

Sensitivity analysis of primary endpoint

After unblinding, the primary endpoint will be analyzed using the Bayesian methods described above as well as conventional statistical methods. The following additional Bayesian analyses will be conducted as sensitivity analyses:

- The primary endpoint will be analyzed regardless of initiation of treatment, or dose adjustment, with AChEIs or memantine using the same Bayesian analysis method as primary analysis. This is an intent-to-treat analysis without any censoring.
- In case of early success, the primary analysis as well as the above sensitivity analyses will be repeated after all subjects have completed 18 months of treatment or have been lost to follow-up.

Statistical methods for the final conventional analyses will use a mixed-effects model with repeated measures (MMRM) on the change from baseline in the derived ADCOMS at

18 months. The model will include treatment groups, randomization stratification variables (the presence or absence of ongoing treatment with AChEIs or memantine or both, and *ApoE4* status), and baseline ADCOMS as covariates. Other covariates such as adjusted hippocampal volume will be studied. These analyses will be performed as sensitivity analyses on the FAS as well as the PP set and as such, no multiplicity adjustments will be made to account for the interim analyses. In case of early success, the conventional analyses will also be performed using the data collected before the interim analysis.

9.7.1.6.2 SECONDARY EFFICACY ANALYSES

The MCI/Prodromal Cohort

An MMRM will be used to analyze the following secondary endpoints:

- Change from baseline in total hippocampal atrophy at 12 and 18 months of treatment in MCI/Prodromal subjects as measured by vMRI
- Change from baseline in CSF A β (1-x) after 4 weeks and 18 months of treatment in MCI/Prodromal subjects. Data from early discontinuations will also be included.

Comparisons between each treatment group and placebo will be performed.

The Mild AD Cohort

The MMRM will be used to analyze the change from baseline of derived ADCOMS at 18 months in mild AD. If there is no treatment group-by-population interaction in the overall study, the MMRM analysis will include all subjects (MCI/Prodromal or mild AD) in the overall study. Otherwise, the MMRM analysis will only include subjects in the mild AD cohort. The comparison between placebo and active doses will be performed within mild AD subjects regardless of subjects included in the MMRM analysis. Dunnett's method will be used to control for multiplicity due to multiple comparisons.

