9.2.5 Rationale for Biomarkers

9.2.5.1 Overall Rationale

The biomarker strategy for this study includes the following aims:

- To establish an amyloid load in the brain at study entry (via the PET eligibility inclusion criterion)
- To evaluate safety (principally by magnetic resonance imaging [MRI])
- To confirm a PD effect in terms of both A β in CSF and brain amyloid assessed by PET and to establish that this PD effect is maintained long-term
- To evaluate disease modification through longitudinal assessments of vMRI, amyloid PET, and CSF biomarkers of neurodegeneration (tau and p-tau)

These aims are discussed below in the context of the individual biomarker assessments to be used in this study.

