9.5.1.4.2 PHARMACODYNAMIC, PHARMACOGENOMIC, AND OTHER BIOMARKER, ASSESSMENTS

Biomarkers

Subjects will be encouraged to stay at the site after completion of LP for medical observation. At Baseline, a CSF sample will be collected by LP (gravity drip method) after fasting (preferred), or at least 2 hours after the most recent meal. The timing of the Baseline LP needs to be scheduled carefully such that subsequent LPs (Visit 7 and Visit 18) can be performed between 4 and 8 hours postdose and at a similar time of day (± 1 hour) for each individual subject. At visits where cognitive tests are also performed, the LP must be performed after the cognitive tests have been completed; the subjects should rest and drink some fluid to hydrate after the cognitive tests and before the LP. The CSF sample will not be taken at the ED Visit if this visit occurs within 3 months of a previous CSF sample. The CSF sample will be used for PD assessments including but not limited to CSF A β (1-x), A β (1-42), t-tau, p-tau, and BACE. The plasma sample will be used for A β (1-x) analysis and may be used for exploratory biomarker analyses (eg, miRNA). A β (1-x) in both CSF and plasma will be measured using a commercially based enzyme-linked immunosorbent assay (ELISA). The pre- and post-screening analysis of CSF A β (1-42), t-tau, and p tau will be performed using ELISAs. BACE1 levels will be measured using internally developed fluorescence resonance energy transfer and ELISA based assay(s). Substrates of BACE1 inhibition may also be explored using Western blots or other amenable methodology if clinical observations warrant and if analytes can be reliably tested in samples collected.

The blood sample collected for PD analyses at Baseline should be collected shortly after completing the LP at Baseline. The sample should be collected at fasting or at least 2 hours after the most recent meal.

At the Baseline Visit, CSF and blood samples will be collected and stored for determination of prior exposure to any suspected infective agents in the event that the subject develops treatment-emergent AEs that warrant further investigation (eg, treatment-emergent infection). Testing may include, but not be limited to, serological tests, viral titer by quantitative polymerase chain reaction, or human leukocyte antigen genotyping.

Blood samples will be collected for PD assessments as specified in [Table 6](#) and [Table 7](#). See Section 9.5.1.4.2 for further details.

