- a: Visit 3 should be conducted 7 to 10 days after completion of the Baseline visit (Visit 2) assessments and confirmation of eligibility to continue in the study, unless additional time is required to take Exclusion Criterion #19 into account. A window of ± 3 days will be permitted for Visit 4 to 14 inclusive. A window of ± 10 days will be permitted for Visit 15 to 18 inclusive. A window of ± 3 days will be permitted for the Follow-Up Visits. If use is made of the permitted visit windows, every effort should be made to bring the subject back in line with the "weeks elapsed since first dose" at subsequent visits.
- b: Subjects who discontinue taking study drug prematurely for any reason will undergo an ED Visit within 7 days of their last dose of study drug. In addition, Follow-Up Visits will be scheduled 4 and 12 weeks after the last dose of study drug (Visit 19 and Visit 20, respectively). Subjects who discontinue study drug prematurely will also be scheduled to return to the study site for each scheduled visit when clinical efficacy assessments are to be conducted (ie. at Visits 11, 14, 15, 16, 17, and 18, if these visits have not already been performed). At these visits, only clinical efficacy assessments (MMSE, CDR, ADAS-cog₁₄, FAQ, CBB, and ISLT) will be conducted. Regularly scheduled clinical efficacy visits do not need to be attended if they fall within 8 days (visit window) after the Early Discontinuation Visit or within ± 8 days of either of the Follow-Up Visits (Visit 19 and Visit 20). Subjects who discontinue early from study drug are considered on study as long as they return for their regularly scheduled clinical efficacy visits as outlined above.
- c: All subjects, regardless of whether they complete all 18 months of treatment or discontinue study drug prematurely, will complete 2 posttreatment Follow-Up visits; one 4 weeks after the last dose of study drug and a second 12 weeks after the last dose of study drug (Visit 19 and Visit 20 respectively). If clinically indicated, more frequent safety assessments can be made as UNS assessments or visits during the posttreatment Follow-Up period.

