- v: All visits at which CSF samples are scheduled to be taken also include blood PK and PD assessments and so the subject will be dosed at the clinic on these days. A CSF sample will be collected by LP between 4 and 8 hours postdose and at the same time of day as the subject's Baseline LP (± 1 hour). The CSF sample will be taken with the subject fasting (preferred) or at least 2 hours after the most recent meal. A gravity drip collection method must be used. The LP will be performed after the cognitive tests; the subject should rest and drink some fluid to hydrate after the cognitive tests and before the LP. Subjects will be encouraged to stay at the site after completion of LP for medical observation. The CSF sample will not be taken at the ED Visit if this visit occurs within 3 months of a previous CSF sample. If at an ED Visit, the subject has already stopped study drug, then no dosing will take place, but the CSF sample will still be collected unless it was already collected within the past 3 months.
- w: Subjects reporting adverse events relating to abnormal dreams, nightmares, or sleep terror will be questioned on the frequency and impact of these events.

x: The first dose of study drug will be given to the subject at the study site and the subject will be encouraged to stay at the site for an appropriate period of time for post-dose medical observation.

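### Early-discontinuation CSF samples enter the amyloid-beta analyses without an on-drug condition, so off-drug values can dilute the 18-month effect and mimic waning

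*Protocol*

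**What the plan says.** The secondary analysis (Protocol 9.7.1.6.2) is an MMRM of change in CSF A-beta(1-x) "after 4 weeks and 18 months of treatment in MCI/Prodromal subjects. Data from early discontinuations will also be included". Section 9.7.1.6.3 attaches the same sentence, "Data from early discontinuations will also be included", to CSF A-beta(1-42) in the MCI/Prodromal cohort and to both A-beta measures in mild AD.

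The sampling rules, mainly in the notes to Table 7, are:

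- Scheduled on-treatment sample: "A CSF sample will be collected by LP between 4 and 8 hours postdose" (note v).
- A subject who stops drug early "will undergo an ED Visit within 7 days of their last dose of study drug" (note b).
- If drug has already been stopped by that visit, "then no dosing will take place, but the CSF sample will still be collected unless it was already collected within the past 3 months" (note v; section 9.5.1.4.1 agrees).
- Section 9.5.1.4.2: "The CSF sample will not be taken at the ED Visit if this visit occurs within 3 months of a previous CSF sample".
- Discontinuers return at later efficacy visits, Visit 18 included, for clinical scales only (note b), so they have no CSF there.

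Section 9.2.5.1 lists among the biomarker aims to confirm the PD effect and "to establish that this PD effect is maintained long-term".

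The protocol file holds two copies of section 9. The off-drug sampling clause is in only one of them, but the sentence that includes ED data is the same in both.

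**The concern.** The endpoint describes the reduction while on treatment, and scheduled samples are tied to a postdose window. The inclusion sentence sets no matching condition for ED samples: no limit on time since last dose and no minimum time on treatment. Elsewhere the protocol does set conditions. Amyloid PET at ED requires at least 39 weeks of drug (9.2.5.3), and for PET and tau section 9.7.1.6.3 uses ED data only as appropriate. The A-beta measures, which should follow current drug level most closely, have no safeguard.

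At stake is the comparison of 18 months with week 4. Week-4 values are drawn on drug. If some 18-month values are not, the effect seems to shrink over time with no true loss, against the stated aim of showing that it is maintained. The size of the reduction by dose at 18 months, and its relation to ADCOMS change (9.7.1.6.3), would be blurred as well.

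**Working it through.** The protocol gives no sample size or power for the CSF endpoint, so there is no stated figure to reproduce. The check has three steps.

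**1. Which time point can ED samples serve?**
- Before week 4: the Baseline puncture lies within the past 3 months, so no ED sample is taken.
- From week 4 to about week 17 (4 + 13 weeks): the Visit 7 puncture lies within the past 3 months, so again none. A subject who missed Visit 7 could be sampled somewhat sooner, but still well after week 4.
- After about week 17: an ED sample is taken. It is the discontinuer's last CSF value, because later visits are clinical scales only.

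Of the two analysed time points, only 18 months is left.

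**2. Direction.** Table 3 predicts A-beta(1-x) reductions of 33%, 56% and 79% at average plasma concentrations of 3.3, 10 and 33.5 ng/ml (5, 15 and 50 mg). Falling exposure means a smaller reduction, so an off-drug sample moves toward baseline. How fast is not given. As an illustration, a Hill curve through the 5 mg and 50 mg rows has slope 0.88 and EC50 7.4 ng/ml, and returns 56.6% at 15 mg against 56% stated. With assumed half-lives of 12, 24 and 48 hours, and effect tracking plasma concentration directly, the 50 mg reduction 3 days after the last dose would be 8.9%, 37.8% and 60.2%.

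**3. Size.** Inputs: 20% attrition at 18 months (9.7.2.1, stated for vMRI; its use for CSF is an assumption), stops spread evenly over 78 weeks, and an ED sample from every discontinuer after week 17.

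ED share of 18-month values:

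s = 0.20 × (61/78) / [0.80 + 0.20 × (61/78)] = 0.156 / 0.956 = 16.4%

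Observed mean reduction = on-drug reduction × [1 − s × q × (1 − r)], where q is the share of ED samples off drug and r the share of the effect still present.

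| q | r | Relative loss | 5 mg | 15 mg | 50 mg |
|---|---|---|---|---|---|
| 0 | – | 0% | 33% | 56% | 79% |
| 25% | 0 | 4.1% | 31.7% | 53.7% | 75.8% |
| 50% | 0 | 8.2% | 30.3% | 51.4% | 72.5% |
| 100% | 0.5 | 8.2% | 30.3% | 51.4% | 72.5% |
| 100% | 0 | 16.4% | 27.6% | 46.8% | 66.1% |

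With q = 100% and r = 0, attrition of 10% gives a relative loss of 8.0% and attrition of 30% gives 25.1%.

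**The case against.** The strongest reply is that the protocol never assigns ED values to the 18-month visit. It says only that they are included, and a SAP that is not shown could give ED its own time point or window visits by day. That stands as a limit: the mapping is an inference. It does not remove the point, because the protocol itself decides inclusion, without condition, in an analysis with two named time points, and only one of those is open to ED samples.

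Second, using discontinuers' data avoids selecting subjects by what happens after randomisation. As a treatment-policy argument this fails. A sample taken within a week of stopping, perhaps near week 20, shows neither the on-drug nor the off-drug state at 18 months. The worry about selection does stand as a reason to keep the all-data version as a sensitivity analysis.

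Third, the protocol partly covers the problem. Dosing and postdose sampling are the default at ED and the undosed draw is the exception (9.5.1.4.1). PK samples are taken even then, and exposure-response work is planned (9.7.1.7.2). That is the right home for off-drug samples, but it does not take them out of the MMRM.

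Two stronger readings are tempting. A reader might apply 20% directly to the 75% target and conclude that the top dose would read 60%, or 15 points low. That ignores the 3-month rule, borrows the vMRI attrition without saying so, and takes every discontinuer to give a fully washed-out sample, although some will be lost to follow-up or withdraw consent. A reader might also infer that Phase 3 dose selection is compromised. The protocol's dose objective is the ADCOMS ED90 (8.1), and its CSF-based dose check uses Stage A week-4 data (9.4.4), which the 3-month rule shields.

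**Conclusion.** The point holds in a limited form. The inclusion sentence and the off-drug sampling clause together allow samples that are neither on drug nor at 18 months into an on-treatment analysis, where the 18-month slot is the only one of the two they can fill. Any off-drug sample biases that value toward baseline and can look like waning against week 4.

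The documents do not fix the size. About 4% to 16% relative loss rests on 20% attrition borrowed from vMRI, even timing of stops, an ED puncture from every eligible discontinuer, and full washout. It shrinks with partial recovery and vanishes if ED samples are drawn on drug, when only their timing is off. A bias of this order would not hide a reduction near 79%, but it could mislead on maintenance and on how the doses compare with their 25%, 50% and 75% targets.

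A reader might infer that the bias differs by dose because safety stops do. That is possible, but the documents do not establish it for 5 to 50 mg. Nor do they give a half-life, a CSF recovery time or a statement that inhibition is reversible.

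**What to change.** In 9.7.1.6.2 and 9.7.1.6.3, replace the unconditional sentence for the CSF A-beta endpoints with the following rules:

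- The main 18-month analysis uses only samples drawn in the protocol's own 4 to 8 hour window after a documented dose.
- An in-window ED sample counts toward 18 months only if it falls in a prespecified 18-month analysis window or after a prespecified minimum time on treatment, as is already done for ED amyloid PET. Otherwise it is not assigned to that time point.
- Subjects with no qualifying 18-month sample contribute their week-4 value through the MMRM.
- Off-drug ED samples are listed and used in PK/PD modelling.
- The all-data version is reported as a sensitivity analysis.

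The cost is wording and a dosing-time flag. The date of last dose is already recorded (9.3.3) and PK samples are already taken at ED (9.5.1.4.1). The downside is somewhat fewer 18-month CSF values in the main analysis.

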[Part 7 of 7 of the document. The other parts are not shown.]

Subjects with mild AD recruited in Stage B will be assessed as a “nested” population that does not follow the Bayesian adaptive design. It was not considered appropriate to have a Bayesian design for both cohorts as this would have substantially increased the overall study sample size, delayed analyses of dose response, and would have added background “noise” for the comparison of subjects with MCI/Prodromal AD compared with those with mild AD. Data from each cohort will be analyzed independently for the purposes of decision making. A separate analysis of the 2 cohorts avoids the risk of data from subjects with mild AD confounding the results for the primary population (MCI/prodromal).

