9.7.2.2 Sample Size Rationale for the Mild AD Cohort

ADCOMS at Month 18

The null hypothesis is that there is no difference between active dose and placebo. There are 2 null hypotheses corresponding to 2 active doses. The alternative hypothesis is that at least 1 null hypothesis is false. The null hypotheses will be tested using Dunnett's test with 2-sided alpha of 0.05 as described for the mild AD cohort in [Section 9.7.1.6.2](#). The statistical power was estimated through simulation for the dose-response assumption that the percent reduction in change from baseline of ADCOMS at 18 months compared with placebo would be 33% and 50% corresponding to the 2 doses, respectively. The estimated power for the actual planned 200 mild AD subjects is at least 80% assuming a 2-sided alpha of 0.05.

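### The mild AD secondary analysis lets an interaction check decide whether MCI/Prodromal subjects enter the model, without saying whether the pooled model keeps treatment-by-population terms

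*Protocol*

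**What the plan says.** Section 9.7.1.6.2 of the protocol (Mild AD Cohort), repeated in the synopsis, sets a two-branch rule for the MMRM of ADCOMS change at 18 months. The first branch is "If there is no treatment group-by-population interaction in the overall study, the MMRM analysis will include all subjects (MCI/Prodromal or mild AD"). The second is "Otherwise, the MMRM analysis will only include subjects in the mild AD cohort". No test or significance level for the interaction is named.

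The paragraph goes on: "The comparison between placebo and active doses will be performed within mild AD subjects regardless of subjects included in the MMRM analysis", and "Dunnett's method will be used to control for multiplicity due to multiple comparisons". It does not list the terms of the pooled model.

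Section 9.2.3, on the choice of design, says: "Data from each cohort will be analyzed independently for the purposes of decision making". Section 9.7.2.2 gives the mild AD power: "The estimated power for the actual planned 200 mild AD subjects is at least 80% assuming a 2-sided alpha of 0.05", for ADCOMS reductions that "compared with placebo would be 33% and 50% corresponding to the 2 doses, respectively".

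**The concern.** The data set for a named secondary endpoint is picked by looking at the data. Failing to find an interaction is weak evidence that there is none, because an interaction contrast is estimated less precisely than the treatment effects it compares. The MCI/Prodromal cohort is planned at up to 500 subjects against about 200 with mild AD. If the pooled model carries one treatment effect for both cohorts, most of the weight in the mild AD result therefore comes from MCI.

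The protocol's aim for the mild AD cohort is to learn whether effects there are comparable with those in MCI (Sections 7 and 9.2.1). A rule that assumes comparability unless a difference is detected partly presumes the answer.

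**Working it through.** **Passages side by side.** Section 9.2.3 promises independent analysis of the cohorts for decisions. Section 9.7.1.6.2 puts both cohorts into one model on one branch. The later sentence confines the comparison to mild AD subjects, but whether that gives a cohort-specific effect depends on model terms the protocol does not state. Two readings are possible.

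**The plan's own power figure.** Section 9.7.2.2 specifies: "The null hypotheses will be tested using Dunnett's test with 2-sided alpha of 0.05". The two-sided Dunnett critical value for two doses against one control is about 2.21. With 200/3 ≈ 67 subjects per arm, 80% power needs a placebo change of about 1.01 SD with no dropout, or about 1.13 SD with 20% dropout. The protocol gives neither the SD nor the placebo change, so the stated power can be neither confirmed nor refuted. At a ratio of 1, the assumed reductions are 0.33 and 0.50 SD and the power is about 79%, close to the plan.

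**Inputs for the two-step rule (assumptions unless sourced).**
- Mild AD: 67 per arm (200 subjects, 1:1:1).
- MCI: 100-150 per shared arm (500/4 = 125 if equal; allocation is adaptive).
- SD 1, and no dropout.
- MCI effect of 0.2-0.4 SD at both shared doses, and mild AD effect zero.
- Interaction test at 5% on 2 degrees of freedom.

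**Formulas.** Let c_M and c_A be the dose-minus-placebo contrasts in MCI and mild AD, with n_M and n_A subjects per arm.
- Interaction: D = c_A − c_M and W = D′V⁻¹D, with V = (1/n_M + 1/n_A) × [[2, 1], [1, 2]].
- Pooled contrast with a population main effect only: c_P = (n_M c_M + n_A c_A)/(n_M + n_A), with standard error √(2/(n_M + n_A)).
- If W is not significant, test c_P; otherwise test c_A, with standard error √(2/n_A). Declare success if either dose exceeds 2.21.

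**Why pooling moves the result.** Take 150 MCI per arm and an MCI effect of 0.3 SD. The pooled contrast has mean (150/217) × 0.3 = 0.207 and standard error √(2/217) = 0.096, so its expected z is 2.16. That is almost at the critical value although the mild AD effect is zero. With 100 per arm and 0.2 SD, it is (100/167) × 0.2 = 0.120 over √(2/167) = 0.109, or z of about 1.1.

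**Results by simulation.**

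| Situation | Treatment effect shared | Mild AD only, or interaction terms kept |
|---|---|---|
| MCI effect 0.2-0.4 SD, mild AD effect zero: false-positive rate | 21% (100/arm, 0.2 SD) to 48% (150/arm, 0.3 SD) | about 5% |
| No effect in either cohort: false-positive rate | about 6-7% | about 5% |
| No MCI effect, mild AD 0.33/0.50 SD: power | about 70%, estimates shrunk 18-19% | 79% |
| Equal effects 0.33/0.50 SD, 125 MCI/arm: power | about 98% | 79% |

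In the first row, the interaction test is significant in only 14-50% of trials.

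**Sensitivity to the assumptions.** A second calculation kept the mild AD effect at zero and used MCI reductions of 15/20/25%, 25/25/25% or 33/33/50%. It varied the placebo change/SD ratio over 0.9-1.1, dropout of 0 or 20%, MCI arms equal or 175/50/100/175, and interaction levels of 0.05, 0.10 and 0.15. With a shared treatment effect the false-positive rate was about 22-49%. With no effect in either cohort it was about 7-8%. With cohort-specific effects it was 4.9-5.1%. A looser interaction level does not rescue the shared-effect version.

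**The case against.** The strongest reply is the sentence that follows the rule: the placebo comparison is made within mild AD subjects whichever data set is used. Read literally, with cohort-specific treatment effects, MCI subjects inform only covariance and covariate terms and the mild AD error stays near 5%. That stands. A reader might infer that a positive MCI result will be reported as a mild AD effect; the protocol does not say so, and it follows only if the treatment-by-population terms are dropped. The reply leaves one thing unexplained: if the contrast is cohort-specific anyway, there is no reason to make pooling depend on the absence of an interaction.

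A test level and model terms may be in the SAP, which is not shown, so their absence is not in itself the fault. The fault is that the protocol fixes a selection rule whose effect turns on those terms.

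The tension with Section 9.2.3 is real but limited. Independence is promised for decision making, the reason given there is to protect the MCI result, and the primary analysis does use MCI/Prodromal subjects only.

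Three further inferences are not supported:
- That pooling happens only when the MCI estimate has been selected to be high. Only the mild AD interims wait for MCI early success; Section 9.7.3 also provides a final analysis without it and an analysis after MCI futility.
- That the power statement contradicts the rule. Section 9.7.2.2 refers to the test described in Section 9.7.1.6.2, and basing power on 200 mild AD subjects is compatible with it.
- That the missing 5 mg arm in mild AD is a defect. The mild AD contrasts concern 15 mg and 50 mg, which both cohorts have.

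Pooling also has a real benefit if the effects are equal, as the last row of the table shows.

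**Conclusion.** The concern holds as a badly fixed analysis rule, not as a demonstrated inflation of error. The protocol lets an interaction check choose the analysis set for the mild AD secondary endpoint, in tension with its own statement on independent analysis, and leaves open the one feature that decides whether this matters. With treatment-by-population terms kept, the check is harmless and pointless. With them dropped, the mild AD false-positive rate is about 21-48% when MCI responds and mild AD does not, and about 6-7% when neither responds. The 21-48% is conditional on the shared-effect model and on the assumed sample sizes, SD, MCI effect and 5% interaction test; the protocol supplies no SD.

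This should be fixed. It concerns a secondary endpoint of a Phase 2 study and leaves the primary analysis untouched.

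**What to change.** In Section 9.7.1.6.2 and the synopsis, state that the mild AD secondary analysis is always an MMRM on mild AD subjects only, with Dunnett adjustment and the group-sequential boundaries (their printed values are a separate matter, not examined here). Delete the interaction check as selector of the analysis set. Keep a pooled MMRM with treatment-by-population terms as a labelled sensitivity analysis of consistency between cohorts. This also brings the text into line with Section 9.2.3.

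The change is to wording in the protocol, and in the SAP where it repeats the rule. The cost is the precision that additive pooling would give if effects are truly equal: about 98% against 79% power at 0.33/0.50 SD with 125 MCI subjects per arm. That gain is not something the plan relies on, since its stated power of at least 80% is already based on the 200 mild AD subjects.
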